5.5. Demography and potential compromising factors

Assessments:

- Baseline/demographics
- Gender
- Age
- Weight
- Height
- Duration of ileostomy/colostomy (year when created)
- Reason for creation of the stoma
- Shape of the stoma
- Size of the stoma (diameter on widest place and height)
- Body profile
- Physical activity
- Sweat
- Output
- Information about the current stoma product
- Normal changing pattern
- Normal main reason for change of product
- Stoma awareness
- Technical ability
- Use of accessories
- Worry about leakage
- Reason for change (continuous)
- Wear time (continuous)

5.6. Equipment/methods and timing for assessing the variables

Assessment data will be captured at V1 by the study nurse who enter the data in the eCRF. Secondary and explorative endpoint data will be captured at V1 and V2, by the subject who will enter the data in the clinical trial app on the provided iPhone.

5.7. Total expected duration of the clinical investigation

The dates below are approximate, and no subjects will be enrolled before all required approvals have been obtained. If changes are required, applicable EC and regulatory authorities will be notified.

- First subject enrolled (04/2021).
- Last subject enrolled (05/2021).
- Last subject completed (06/2021).
- Final report (06/2022).

6. Clinical Investigation population

The clinical investigation will be conducted in 25 subjects enrolled from one clinical investigation site.

Due to the conceptual nature of this trial no formal sample size calculation has been performed. It is assumed that 25 subjects will be adequate for evaluating the sensor performance. Drop-out subjects will not be replaced.

We strive to include an equally number of users in the categories 1pc, 2pc, flat, convex and concave.

6.1. Eligibility criteria

To be included in the investigation, the subjects must comply with the selection criteria described below

6.1.1. Inclusion criteria

Inclusion criteria:	Inclusion:

1. Have given written informed consent
 
2. Be at least 18 years of age and have full legal capacity
 
3. Have had a stoma for more than three months
 
4. Have intact skin on the area used in the evaluation meaning no broken skin and only minor discoloration of the skin (assessed by investigator)
 
5. Be able to use one of the five test products (i.e. Ø40, Ø50, Ø60, Ø70, Ø80 mm)
 
6. Ileo- or colostomists with liquid output (Bristol scale type 6-7).
 
7. Currently using a Coloplast product (1pc/2pc Flat/Convex/Concave) from e.g Assura/Sen-Sura/SenSura Mio
 
8. Have self-reported problems with leakage* (three times within 14 days)
 
9. Have worry of leakage 'to some, high or very high degree'
 
10. Is familiar with the use of a smartphone
 
*Leakage: Leakage is defined as output from the stoma on the backside of the baseplate (underneath the baseplate)
	
1. To meet the Helsinki Declaration
 
2. To meet the Helsinki Declaration
 
3. Recovered from ostomy surgery
 
4. The skin must be intact, otherwise the product will change classification category.
 
5. The technical design of the device requires use of one of the five sizes
 
6. The technical design of the device requires liquid output
 
7. To minimize unknown factors from competitor adhesives, only users of Coloplast products can be enrolled in this study.
 
8. The sensors in the product will only be activated by moist/leakage so in order to be able to evaluate the product the subjects need to have a certain amount of leakage.
 
9. Users who do not worry of leakage at any or low degree are excluded.
 
10. Users who do not know how to maneuver a smartphone will have to large difficulties in using the product and will also not be able to use the product going forward as it requires that the user has a smartphone.

6.1.2. Exclusion criteria

Exclusion criteria	Exclusion:

 1. Currently receiving or have within the past 2 month received radio- and/or chemotherapy 2. Currently receiving or have within the past month received topical steroid treatment in the peristomal skin area or systemic steroid (tablet/injection) treatment. 3. Are pregnant or breastfeeding** 4. Participating in other interventional clinical investigations or have previously participated in this investigation. Exception: Participation in other Coloplast sponsored clinical investigations is accepted under the circumstances that the subject has paused the activities in the investigation and are otherwise complying with the inclusion and exclusion criteria of this protocol. 5. Known sensitivity towards test product 6. Known sensitivity towards acrylate 7. Is using/have a pacemaker 8. Is using ostomy paste or ostomy powder 	
 1. The skin undergoes major changes because of radio- and/or chemotherapy, and therefore it can be more fragile to base plate changes 2. Steroid product may interfere with the study end points by making the peristomal skin thinner and more fragile 3. Even though the ingredients and the recipes have been approved for human beings, their effect on embryos, fetuses and infants are unknown 4. Other interventional investigation guidelines/products may interfere with these investigational endpoints. Some of the Coloplast studies are taking place over a two-year period, where the subjects will be paused for longer periods between the visits - therefore they are allowed to participate in other Coloplast studies meanwhile. 5. To protect subjects wellbeing 6. To protect the subjects from unnecessary harm 7. To protect the subjects from unnecessary harm users with a pacemaker are excluded 8. The use of ostomy paste or ostomy powder may influence system performance and is excluded in this study

** Besides a negative pregnancy test the women must also commit to use safe contraceptives during the study period (i.e. contraceptive coil, hormone base contraceptives or surgical sterilisation). However, in some cases when the women are older than 50 years, but are not yet post-menopausal, the investigator may evaluate that it is not reasonable to ask these women to start using safe contraceptives for the duration of the investigation (e.g. if the subject is abstinent, the partner is surgically sterilised, or either subject or partner is infertile). In these cases, the investigator can include the woman, but has a responsibility of ensuring that he/she has done what he/she can to prevent these subjects from becoming pregnant. As a minimum investigator must talk to the women about the risk of and how to avoid unwanted pregnancy at inclusion and at every visit hereafter.

Subjects who uses a mouldable ring may be included, if able to fit one of the five test products while wearing the ring. The sensor layer should be applied to the peristomal skin, not covering the ring.

6.2. Recruitment and enrolment

Recruitment of potential subjects will begin once approval have been obtained from the Ethics Committee and the Danish Medicines Agency

Recruitment method		Advertisement
Potential subjects		

	ileostomy or colostomy and be at least 18 years of age.	
First contact		Interested subject contact the investigator or delegated study personnel
Second contact	If potential subjects return the Reply Letter/reply to the email, or have called the investigator as first contact and are interested, the Investigator or delegated site personnel will contact the subjects by phone and give a short introduction to the investigation and go over the inclusion and exclusion criteria. If the subjects do not meet the inclusion criteria or meet the exclusion criteria, this will be registered in the Subject Screening Log.	
Subject Information Form	If subjects are eligible and interested in participating, then written information about the investigation (subject information) will be sent to the subjects to ensure that they are given the opportunity to read about the investigation before a possible informational visit, and so that they can prepare any possible questions they may have. Information visit V0 will be booked at this point and the subjects are instructed to contact the investigator or delegated study personnel if they, after having read the subject information, no longer are interested in participation in the study.	
First visit Information visit	If an eligible subject is interested in participating, information visit (V0) will be arranged either remotely or in a room ensuring quiet surroundings. That could either be in the subject own home or at Coloplast if preferred by the subject. When arranging the visit, it will be ensured, that the subject has received the Subject Information prior to the visit. The subjects will receive both written and verbal information about the possibility of bringing a companion to the informational visit and to any possible subsequent visits. See section Error! Reference source not found. for information to be given to the subjects, as well as the informed consent process.	
Enrolment and inclusion visit (V0)	The subjects have the right to wait 24h before deciding on participation. If/when the subject decides to participate he/she will be asked to sign the relevant forms (see section 13). If a subject so desires, and it is certain that it is understood what the investigation entails and the relevant forms have been signed the subjects are considered enrolled in the investigation.	

It is estimated that the recruitment process will be completed within 8 weeks.

6.3. Subject withdrawal criteria

The subject is allowed to withdraw from the investigation at any time for whatever reason without any consequences for their future treatment outside the clinical investigation. The Investigator may withdraw a subject from the investigation at any time if they judge it to be the subject's interest.

The investigator must withdraw a subject from the investigation due to:

- Noncompliance with the CIP impacting the scientific integrity of the investigation.
- If subject's safety and wellbeing is compromised by further participation.
- Subjects lost to follow-up. At least three documented attempts will be made to verify subjects lost to follow-up.

Withdrawn subjects will not be replaced by new subjects.

A subject who is withdrawn from the investigation, for any reason, will be encouraged to contact the investigator if problems arise that the subject believes are related to the clinical investigation. Subjects who have not experienced any adverse events will not be followed up. For subjects who experience adverse events, see section 18.

6.4. Point of enrolment

A subject is considered enrolled in the investigation when the written informed consent is obtained. The expected duration for each subject is described in section 5.7

6.5. Subject Identification and Confidentiality

Subjects will be identified on the electronic CRF (eCRF) and any other document transmitted to the sponsor by the principal investigator or clinical site staff, by a unique identification number.

Data entered in the eCRF are confidential and will only be available to the sponsor (including sponsor delegates), members of data management teams, the statistician, members of the EC and if requested to regulatory authorities.

The principal investigator for each clinical investigation site will maintain as part of the investigational file a list identifying all subjects entered into the clinical investigation.

7. Procedures

7.1. Clinical investigation-related procedures

7.1.1. Visits

All visits (V) will be planned to be remote visits using Microsoft Teams, Skype or Face time, if technically possible. If a remote visit is not possible, a face to face meeting will be scheduled, either at subjects' own home or at Coloplast A/S, Humlebæk.

Visit 0 (Inclusion visit)

If a potential subject is interested in participating after the first contact and they met screening and inclusion criteria, a visit (visit 0) is arranged. When arranging the visit, it will be ensured, that the subject has received the Subject Information Form prior to the visit. The subjects will receive both written and verbal information to ensure that the subject understands what was read and explained and can freely agree to participate in the investigation. The subject will, beforehand, also be informed about the possibility of bringing a companion to Visit 0 and to any possible subsequent visits. During the visit the principal Investigator, or delegate, will provide oral information about the investigation based on the Subject Information Form. The subject has the right to wait before deciding on participation.

If/when subjects decide to participate, they will be asked to sign the Informed Consent Signature Form. Hereafter, relevant female subjects will be asked to take a pregnancy test. If a subject so desires, and it is certain that it is understood what the investigation entails, and the relevant form has been signed, the subjects are considered enrolled in the investigation. Enrolled subjects are allocated a subject number. Visit 0 and visit 1 can be combined.

Visits (V1)

During visit 1, baseline questions will be completed by the Principal Investigator, or delegate. The subject will be trained in the use of the clinical trial app, which is used for taking photos of used products at each product change, and how to complete the questions prompted at product change. The Principal Investigator, or delegate will ensure questions relevant for visit 1 are completed. At visit 1 the subjects will also thoroughly be trained in the use of the test product and instructed to continue their everyday life.

Visits (V2)

During visit 2, potential (S)AE's will be captured by the Principal Investigator, or delegate. During visit 2, the Principal Investigator, or delegate will ensure questions relevant for visit 2 are completed, hereafter termination.

Visits (Vx)

If circumstances demand it e.g. due to specific issues with the test product, an additional visit may be scheduled. In section 7.2 Flow-chart, assessment and endpoints are specified.

7.2. Flow-chart

Table 1 chart showing the connection between visits and assessments.

	Registration/measurement	PERFORMED BY	INFOR-MATION MEETING	SCREEN-ING	VISIT 1	VISIT 2 TERMI-NA-TION	CON-TINUOUS LY
	General						
	Oral information	Investigator	X				
	Written informed consent	Investigator	X	X			
	Check of in- and exclusion criteria	Investigator		X			
	Insurance of subjects' wellbeing and compliance with CIP	Investigator		X	X		
	Registration of Demographics/assessments						
	
 • Gender • Age • Weight • Height • Duration of ileostomy/colostomy (year when created) • Reason for creation of the stoma • Shape of the stoma • Size of the stoma (diameter on widest place and height) • Body profile • Physical activity • Sweat • Output • Information about the current stoma product • Normal changing pattern • Normal main reason for change of product • Stoma awareness • Technical ability • Use of accessories 	Investigator			X		
	
 ○ Wear time ○ Reason for change 	Subject					X X

No.	Registration/measurement	PERFORMED BY	INFOR-MATION MEETING	SCREEN-ING	VISIT 1	VISIT 2 TERMI-NATION	CONTINUOUS LY
	Primary endpoint						
1	To evaluate system performance focusing on accuracy of data classification into true positive and true negative	sponsor representa-tive (evaluate pic-tures, assess leak to sensors) Subject (takes pic-tures at each change)					X
	Secondary endpoint(s)						
2	Frequency of leakage onto clothes	Subject			X	X	
3	Overall experience of leakage onto clothes with test product compared to only using usual product	Subject				X	
4	Reliability of notifications	Subject				X	
5	Ability to move with test product	Subject				X	
6	Subjects worry of leakage	Subject			X	X	
7	Confidence to avoid leakage onto clothes with test product compared to only using usual product	Subject				X	
8	Confidence in daily life compared to only us-ing usual product	Subject				X	
9	Feeling of control with test product com-pared to only using usual product	Subject				X	
10	Control of leakage progression with test product compared to only using usual prod-uct	Subject				X	
11	Feeling of security with test product com-pared to only using usual product	Subject				X	
12	Evaluation of confidence to increase social activities with test product compared to only using usual product	Subject				X	
13	Evaluation of sleep with test product com-pared to only using usual product	Subject				X	
14	Confidence at night with test product com-pared to only using usual product	Subject				X	
15	Preference	Subject				X	
16	Reason for preference	Subject				X	
17	Evaluation of users' peace of mind with test product	Subject				X	
18	To evaluate users' assessment of QoL with test product compared to usual product	Subject				X	
19	Adhesive residue to skin	Subject				X	
20	Adhesive residue to transmitter	Subject				X	
	Exploratory endpoints						
Appx 1	HRQoL evaluation	Subject			X	X	
Appx 2	OLI evaluation	Subject			X	X	
21	Evaluation of self-management (predictabil-ity of change) of stoma appliance compared to usual product	Subject				X	

	Registration/measurement	PERFORMED BY	INFOR-MATION MEETING	SCREEN-ING	VISIT 1	VISIT 2 TERMI-NA-TION	CONTINUOUS LY
22							
23							
	Registration of termination						
	AEs/ADEs/SAEs/SADEs	Investigator		X	X	X	X
	Termination form	Investigator					X

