Primary endpoint and secondary endpoint(s)

Primary endpoint:

- The primary endpoint is to evaluate system performance focusing on accuracy of data classification into true positive and true negative

Secondary endpoints:

- Frequency of leakage onto clothes before and after use of test product
- Experience of leakage onto clothes compared to only using usual product
- Reliability of notifications
- Ability to move with test product
- Subjects worry of leakage before and after use of test product
- Confidence to avoid full leakage with test product compared to only using usual product
- Confidence in daily life compared to only using usual product
- Feeling of control with test product compared to only using usual product
- Control of leakage progression with test product compared to only using usual product
- Feeling of security with test product compared to only using usual product
- Evaluation of confidence to increase social activities with test product compared to only using usual product
- Evaluation of sleep with test product compared to only using usual product
- Confidence at night with test product compared to only using usual product
- Evaluation of users' preference
- Reason for preference
- Evaluation of users' peace of mind with test product
- To evaluate users' assessment of QoL with test product compared to usual product
- Adhesive residue to transmitter
- Adhesive residue to skin

Population/subjects

We will include n=25 subjects as a minimum of 25 subjects are needed to evaluate sensor performance and to have a potential support of relevant core claims.

N=15 subjects will get the test product app on an Android phone and n=10 users will get the test product app on an Iphone.

We strive to include an equally number of subjects in the categories 1pc, 2pc.

Subjects may use any Coloplast baseplate (Assura, SenSura, SenSura Mio) flat, convex and concave
Up to 5 subjects may use a mouldable ring (see exclusion criteria)

Inclusion criteria:

1. Have given written informed consent
2. Be at least 18 years of age and have full legal capacity
3. Have had a stoma for more than three months
4. Have intact skin on the area used in the evaluation meaning no broken skin and only minor discolouration of the skin (assessed by investigator)
5. Be able to use one of the five sensor layer sizes (i.e. Ø40, Ø50, Ø60, Ø70, Ø80 mm)
6. Ileo- or colostomists with liquid output (Bristol scale type 6-7).

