5.4. Rationale for selection and measurement of endpoints

The endpoint of system performance has been selected as primary endpoint in this investigation as this is the core performance measure of the system. The objective measure of leak notification accuracy (system performance) will be obtained by comparing leak areas from pictures of the backside of the adhesive baseplate to the output leak notifications received by the subjects for each of the leak sensor areas.

Secondary endpoints are related to users experience of reliability of leak notifications as well as users experience of what the product might offer them to support control, confidence and feeling of security in everyday life and whether it may help to reduce their worry of leakage, especially leakage onto clothes.

Secondary endpoints related to user experience with use of test product are asked on five-point Likert scales or as yes/no questions.

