10.1. Statistical design, method and analytical procedures

Definition of analysis populations

Intention to Treat (ITT) and Safety populations will be defined at a formal data review meeting just before database lock. As a minimum, the data manager, the clinical manager and the statistician will be involved in the classification of subjects.

The ITT population (full analysis set) will be constituted by all included subjects who:

- Have provided valid informed consent
- Have information for at least one of the endpoints

The Safety population will constitute by subjects who have given informed consent.

All statistical analysis and summaries will be based upon the ITT population whereas adverse events and Device deficiencies will be assessed based on the safety population. Invalid individual data points may be omitted from analysis even though the corresponding subject is part of the ITT population. Any exclusion of data points will be documented.

A formal PP population is not planned due to the explorative nature of the investigation. Considering the data obtained it might however be considered to make additional explorative analyses based on a subset of the ITT population.

Analysis of endpoints, individual questions and baseline data

All endpoints and individual questions as well as baseline/demographic data will be listed and summarized by descriptive statistics. Summaries can be made for 1- and 2-piece users as well as for the subgroups (flat, convex and if relevant concave) or (iPhones, Androids), if relevant.

The accuracy of the sensor performance will be calculated based on picture data used to correlate notifications given with output to sensors on baseplates (primary endpoint). The accuracy will be calculated by dividing the true positive plus the true negative with the total sum of the true positive, true negative, false positive and false negative.

For secondary endpoints where the possible answer is Yes or No, the proportion of subjects answering "Yes" will be calculated. By use of an exact test in the Binomial distribution a 95% confidence interval will be estimated for the proportion. Further, it will be tested if the proportion is significantly different from 50% when using a 5% test level. For questions answered on a 5-point scale the answers can be grouped in 2 (e.g. "higher" or "much higher" against the rest of the answers) and analyzed by the above described method.

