10.4. Pass/fail criteria

No formal success criteria are applied in this investigation. Study results may be used for relevant claims.

The study will provide valuable insight into the performance and safety of the device and the ability to support the user with useful information regarding potential leakages in an everyday life setting.

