10.5. Interim analysis

There is no planned interim analysis in this investigation that will affect the evaluation of the objectives. To facilitate and optimize the development of improved versions of the algorithm engineers working with the software will get restricted access to data before DBL. The result of their work will be for internal optimization of future versions of the algorithm only and will not be reported before after the result meeting of the study.

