18.3. Device deficiency

A device deficiency is the inadequacy of the investigational medical device or comparator with respect to its identity, quality, durability, reliability, safety or performance. This includes malfunctions, use errors and inadequacy in the information supplied by the manufacturer including labelling.

Example: Transmitter not able to charge.

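### The photo reading behind the primary accuracy is neither masked to the notifications nor fixed before linkage, and undefined invalid points may be omitted, so the figure is open to review bias and selective omission

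*Combined protocol and SAP*

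**What the plan says.** Section 5.4 describes the primary measure as objective and says that it is obtained by "comparing leak areas from pictures of the backside of the adhesive baseplate to the output leak notifications received by the subjects", sensor area by sensor area. The primary endpoint row of the flow-chart in section 7.2 divides the work: the subject photographs the product at each change, and the reading falls to a "sponsor representa-tive (evaluate pic-tures, assess leak to sensors".

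Section 10.1 defines accuracy as true positives plus true negatives, divided by the sum of all four cells. It says that picture data are used to relate notifications to output on the sensors, but gives no order for the reading and the linkage. On exclusions it says "Invalid individual data points may be omitted from analysis even though the corresponding subject is part of the ITT population", followed by "Any exclusion of data points will be documented". It does not define an invalid point.

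Sections 10.1 and 11.1.2 provide for a data review meeting before database lock, and 11.1.2 for role-based access and an audit trail. Section 3.1 calls the study exploratory with no formal hypotheses. Section 10.4 sets no success criterion but adds "Study results may be used for relevant claims".

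**The concern.** A leak on a used baseplate can be faint, partial or near the edge of a sensor area, and someone must then decide whether output reached that sensor. If the person deciding knows whether a notification was sent, that knowledge can settle the doubtful cases. The reference standard is then no longer independent of the device it is meant to judge.

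Omission raises the same problem. If a point can be called invalid after its agreement with the notification is known, the choice can depend on that agreement. Documenting the exclusion shows that it happened; it does not prevent the dependence.

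What is at stake is how far the single primary result can be trusted. More subjects or more photos would not remove a shift of this kind; they would only estimate the shifted value more precisely.

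**Working it through.** **No plan figure to reproduce.** The plan states no expected accuracy, margin or power. The 25 subjects are an assumption (sections 10.2 and 10.3). All numerical inputs below are therefore mine and serve only as illustration.

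**Step 1: look for a safeguard.**
- Section 7.2 says who reads, but not what information the person has.
- Section 5.4 says what is compared, but not in which order.
- Section 7.3 refers to section 10.1 for details of data capture, but 10.1 contains no reading procedure.
- The data review meeting in section 10.1 is described as classifying subjects into populations. It is not said to be masked or to come before linkage.
- The access control and audit trail in section 11.1.2 govern and record actions in the system. They do not withhold notifications from the photo reader.
- The separate phones in section 4.6 separate the devices. Nothing says that they separate the information reaching the photo reader.

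No section requires masked reading, fixes the readings before linkage, or limits omissions beyond documentation.

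**Step 2: omission.** Let A be the accuracy with nothing omitted, x the share of discordant points omitted and y the share of concordant points omitted. From the formula in section 10.1,

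apparent accuracy = A(1 − y) / [A(1 − y) + (1 − A)(1 − x)].

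| A | x | y | Calculation | Apparent accuracy |
|---|---|---|---|---|
| 0.80 | 0.10 | 0 | 0.80 / (0.80 + 0.18) | 81.6% |
| 0.80 | 0.20 | 0 | 0.80 / (0.80 + 0.16) | 83.3% |
| 0.80 | 0.30 | 0 | 0.80 / (0.80 + 0.14) | 85.1% |
| 0.80 | 0.20 | 0.10 | 0.72 / (0.72 + 0.16) | 81.8% |
| 0.80 | 0.20 | 0.20 | 0.64 / (0.64 + 0.16) | 80.0% |
| 0.80 | 0.10 | 0.20 | 0.64 / (0.64 + 0.18) | 78.0% |
| 0.90 | 0.20 | 0 | 0.90 / (0.90 + 0.08) | 91.8% |

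Omission that falls mainly on discordant points raises the figure, equal rates leave it unchanged, and omission mainly of concordant points lowers it.

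**Step 3: reading.** The effect of masking is the difference between unmasked and masked reading of the same areas. Let a be the share of areas that are ambiguous, and p the share of these read as agreeing with the notification. Then

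change in accuracy = a × (p_unmasked − p_masked).

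- a = 0.10, p_masked = 0.80, p_unmasked = 1.00: 0.10 × 0.20 = +2.0 points.
- a = 0.20, same p: 0.20 × 0.20 = +4.0 points.
- a = 0.10, p_masked = 0.50, p_unmasked = 1.00: 0.10 × 0.50 = +5.0 points.
- a = 0.10, p_masked = 0.80, p_unmasked = 0.70: 0.10 × (−0.10) = −1.0 point.
- p_unmasked = p_masked: no change.

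The documents give none of a, p_masked or p_unmasked.

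**The case against.** The reading half of the point rests on silence. Section 7.2 gives the photo reader one task, and section 5.4 can be read as making the comparison a separate operation. Photos come through the Clinical Trial app on its own iPhone (sections 4.6 and 11.1.1), while notifications go to the product phone. The reason-for-change answer in Appendix 4 would reveal at most that some notification occurred, and no section sends it to the photo reader. Masking may also be set out in a working document that is not part of the plan. All of this stands: the documents do not show that the reader sees the notifications. But a workflow that may happen to be masked is not a requirement, and the omission rule in section 10.1 is explicit text rather than silence.

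The study is also exploratory, has no success criterion, and plans no test of accuracy. Section 3.1 ties commercial claims to user experience. This limits the priority. It does not remove the point, because section 10.4 allows results to be used for claims without excluding accuracy.

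Three stronger readings are tempting, and the documents do not support them.
- One might infer that the accuracy will be inflated. An upward shift needs a reader who leans towards the notification, or omission mainly of discordant points. The plan shows neither, and the sign can reverse.
- One might infer from section 10.5, where "engineers working with the software will get restricted access to data before DBL", that readings could be altered before lock. That access is restricted and serves future versions of the algorithm only. Nothing there concerns photo reading or omissions.
- One might infer from section 18.3 ("Example: Transmitter not able to charge") that device failures would be dropped as invalid. That section defines device deficiencies and does not call them invalid data points; section 10.1 assesses them separately in the safety population.

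**Conclusion.** The point holds as a gap in what the plan requires. The primary accuracy depends on a sponsor reading that need not be made without the notifications or fixed before linkage, and on an omission rule with no definition and no condition other than documentation. The figure is open to review bias and selective omission.

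Neither size nor sign follows from the documents. In the illustrations, omission moves a true 80% to between 78.0% and 85.1%, and unmasked reading shifts accuracy by between −1.0 and +5.0 points. These ranges rest wholly on assumed inputs and are not estimates for this study. Priority is modest: the change is a cheap improvement to the only primary endpoint of an exploratory study.

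**What to change.** Amend sections 5.4, 7.2 and 10.1 as follows.

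1. The existing readers receive coded photos without notification, sensor-signal or reason-for-change data. For each sensor area they record leak or no leak, and whether the photo is valid.
2. This record is locked before it is merged with the notification log.
3. Photo-based omissions rest only on the masked validity call. Any other omission follows a criterion written before linkage and applied without knowledge of agreement.
4. The report gives the number of points omitted by reason, and a second accuracy figure that includes omitted points where they can be classified. This table may be sparse, since an unreadable photo has no reference reading; the counts by reason then carry the information.

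The cost is photo coding, one validity field, a written omission criterion, one lock step, one extra table and slightly longer data preparation. No extra readers, visits or subject burden are needed. Masking removes dependence on the notification; it does not remove ordinary reading error. If masked reading is already intended, one sentence in the plan settles that part.
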